C The study is event driven. The number of confirmed adjudicated primary endpoint events will be continuously monitored during the trial. Based on the available number of events the projected number of expected future events will be calculated. As soon as the projection reliably suggests that the total number of patients with a by adjudication confirmed primary endpoint event will reach 625 **611 within the next 24 weeks**, the trial team will perform respective actions to stop the trial. From this time point on, all patients are expected to perform their last visit (EOT visit) within the **regular proposed** time schedule, **which means within the next 24 weeks communicated via an investigator letter**. A follow-up visit will take place **one week 30 days** after the end of treatment (EOT visit).

Patients who discontinue study drug prematurely should continue study visits until study end. Study assessments may be omitted if a patient is willing to return to the pre-defined study visits, with exception **collection of adverse events, outcome events, concomitant therapy and laboratory testing of creatinine for the calculation of the eGFR**.

If a patient who prematurely discontinued study drug is not willing to return to the pre-defined study visits, at minimum a yearly telephone call (preferably every 6 months) and a telephone call at study end will be required, to document the occurrence of outcome events and vital status. If possible, other adverse events and concomitant therapy changes since last visit **might should** be recorded (refer to [section 3.3.4](#)).

D All patients will have a follow up visit **one week 30 days** following regular or premature completion of the treatment period. The follow-up visit may be performed as a phone visit for patients who did not prematurely discontinue study medication and who do not have abnormalities at the EOT visit (only adverse events/outcome events and changes in concomitant therapy to be obtained).

E Body Mass Index will be calculated automatically.

F A complete, head-to-toe physical examination (e.g. evaluation of the body and its functions using inspection, palpation, percussion, and auscultation) will be done.

G

H In addition to the visits indicated, electrocardiogram (ECG) should be recorded in case of respective cardiac symptoms (indicating rhythm disorders or cardiac ischemia).

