### 3. DESCRIPTION OF DESIGN AND TRIAL POPULATION

#### 3.1 OVERALL TRIAL DESIGN AND PLAN

This randomized, double-blind, and placebo controlled study compares treatment with linagliptin (5 mg once daily) with placebo treatment (matching tablets once daily) as add-on therapy to standard of care background antidiabetic treatment as specified in [Section 3.3.2](#).

The trial is event driven and will run until 625 **611** patients with a by adjudication confirmed primary endpoint event are observed ([Section 7.6](#)), with an estimated 8300 **7000** randomized patients to be observed for an estimated study duration of 48 **54** months, beginning with the randomization of the first patient. The anticipated recruitment period is 36 months. In case the number of primary endpoint events is not or may not be reached within this period the trial duration ~~and/or the number of patients~~ will be increased until the defined number of adjudicated primary endpoint events is reached.

[figure not shown]

Figure 3.1: 1 Treatment periods and treatment groups in the trial design

For all patients, site visits are scheduled at regular time intervals (see [flow chart](#)). The estimated treatment duration for the first randomized patient is 48 **54** months. The number of confirmed adjudicated primary endpoint events will be continuously monitored during the trial. Based on the available number of events the projected number of expected future events will be calculated. As soon as the projection reliably suggests that the total number of patients with a by adjudication confirmed primary endpoint event will reach **625 611** ~~within the next 24 weeks~~, the trial team will perform respective actions to stop the trial. From this time point on, all patients are expected to perform their last visit (EOT visit) within the ~~regular proposed~~ time schedule, which means ~~within the next 24 weeks~~ **communicated via an investigator letter**.

The End of Treatment visit (EOT) activities will be performed when a patient discontinues study medication treatment permanently. The EOT activities are not required for temporary interruptions of study drug. All patients will have a follow up visit ~~one week~~ **30 days** following discontinuation of study drug, irrespective whether they complete the treatment period or pre-maturely discontinue study treatment. Patients who discontinue study drug prematurely should continue study visits until study end. Study assessments may be omitted

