
Proprietary confidential information.

© 2016 Boehringer Ingelheim International GmbH or one or more of its affiliated companies. All rights reserved.

This document may not - in full or in part - be passed on, reproduced, published or otherwise used without prior written permission.

if a patient is willing to return to the pre-defined study visits, with exception of collection of adverse events, outcome events, concomitant therapy and laboratory testing of creatinine for the calculation of the eGFR.

If a patient who prematurely discontinued study drug is not willing to return to the pre-defined study visits, at minimum a yearly telephone call (preferably every 6 months) and a telephone call at study end will be required, to document the occurrence of outcome events and vital status. If possible, other AE's and concomitant therapy changes since last visit might be recorded. Every attempt will be made by the investigator to ensure patients continue participating in the study during study drug interruptions and after discontinuation of study drug. The ITT analysis requires that all study patients be followed until study end even if the study drug was temporarily interrupted or discontinued.

Patients will have a follow up visit ~~one week~~ **30 days** following regular or premature completion of the treatment period. The follow-up visit may be performed as a phone visit for patients who did not prematurely discontinue study medication and who do not have abnormalities at the EOT visit (only AEs/outcome events and changes in concomitant therapy to be obtained).

In case early study termination is to be performed (e.g. based on recommendation by the Data Monitoring Committee [DMC]), a reasonable timeframe to stop the trial (perform last patient visits) will be defined and communicated to the investigators.

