**Early discontinuation of study medication is not a criterion for withdrawal of consent for participating in the study.**

If a patient becomes pregnant during the trial, the study treatment will be stopped, the patient will be followed up during the study and until birth or termination of the pregnancy (see further details in [Section 5.2.2.2](#)).

If pancreatitis is suspected, the study treatment should be stopped.

**An individual patient is to be withdrawn from the study and follow up assessments only if the patient actively withdraws consent, without the need to justify the decision.**

Proprietary confidential information.

© 2016 Boehringer Ingelheim International GmbH or one or more of its affiliated companies. All rights reserved.

This document may not - in full or in part - be passed on, reproduced, published or otherwise used without prior written permission.

A patient has the right to withdraw informed consent for participation at any time for any reason. However, withdrawal of consent from study participation should be very rare and unusual. Because of this, the investigator should be involved in the discussions with the patient regarding a withdrawal of consent. Additionally, the investigator should discuss the withdrawal of consent with the sponsor representative prior to stopping study participation.

Patients that are not actively taking study drug may be less motivated to adhere to the study visit schedule. Investigators and site staff should work to detect early signs of losing interest and readily present such patients (not actively taking study drug) with the following options to encourage continued participation:

- Option 1 Continue to attend regularly scheduled study visits at the site until the study ends
- Option 2 Conduct all remaining study visits over the phone
- Option 3 Discontinue participation in remaining study activities but permit collection of vital status and CV outcome events at minimum at the end of the study through the patient or alternative person designated by the patient (e.g., family, spouse, partner, legal representative, or physician) even if only by telephone
- Option 4 Discontinue participation in remaining study activities but permit collection of vital status at minimum at the end of the trial through the patient, alternative person designated by the patient, or through review of patient's medical information from alternative sources (e.g., doctor's notes, hospital records, etc.)

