## 5. VARIABLES AND THEIR ASSESSMENT

### 5.1 EFFICACY

#### 5.1.1 Endpoint(s) of efficacy

The primary endpoint in this trial is time to the first occurrence of any of the following **by adjudication confirmed** components of the primary composite endpoint (4 **3**-point MACE): CV death (~~including fatal stroke, fatal MI and sudden death~~), non-fatal MI (~~excluding silent MI~~) **or** non-fatal stroke and hospitalisation for ~~unstable angina pectoris~~.

**The key secondary endpoints are** **is** time to the first occurrence of **any of the following by adjudication confirmed components:**

- CV death (~~including fatal stroke, fatal MI and sudden death~~), non-fatal MI (~~excluding silent MI~~), non-fatal stroke (**3**-point MACE)
- Composite renal endpoint (renal death, sustained ESRD, sustained decrease of **50 40%** or more in eGFR)

~~At the final analysis the~~ **The** primary endpoint (4 **3**-point MACE) will be tested for non-inferiority. Thereafter, **if non-inferiority has been demonstrated**, the 4 **3**-point MACE and the combined composite renal endpoint will be tested separately (~~= in parallel~~) for superiority. ~~In case the 4-point MACE and/or composite renal endpoint is significantly superior, the 3-point MACE will then be tested for superiority.~~

Even after occurrence of a non-fatal endpoint, the patient should be followed-up until the end of the study in order to document other endpoints/variables.

Proprietary confidential information.

© 2016 Boehringer Ingelheim International GmbH or one or more of its affiliated companies. All rights reserved.

This document may not - in full or in part - be passed on, reproduced, published or otherwise used without prior written permission.

\* Silent MI is an investigator reported endpoint, and is a trigger term for central adjudication for cardiovascular events. Any investigator reported silent MI that is adjudicated and confirmed as being an MI by the CEC will be counted as MI.

Proprietary confidential information.

© 2016 Boehringer Ingelheim International GmbH or one or more of its affiliated companies. All rights reserved.  
This document may not - in full or in part - be passed on, reproduced, published or otherwise used without prior written permission.

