#### *Visit 3 – EOT - FU*

- Clinical chemistry: creatinine and lipase
- Urine analysis: albumin and creatinine (visit 4, visit 6 and thereafter yearly).
- Clinical chemistry: cholesterol (total), HDL cholesterol, LDL cholesterol and triglycerides (visit 4, visit 6 and thereafter yearly)

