# 7.8.1.7 Events qualifying for external adjudication by the Clinical Event Committee (CEC)

Tabulations with frequency of patients with AEs triggering CEC adjudication (based on specified Standardized MedDRA Queries (SMQs) according to CEC charter and manually identified) will be provided by treatment group and overall, by primary SOC and preferred term. All events will be taken into account from first study drug intake up to study end. This table will be provided separately for cardio/neuro, renal, pancreatic adjudication and oncological assessment.

Further, outcome events captured by the investigators will be contrasted with those defined by the adjudication committee.

For cardio- and cerebrovascular events the components as listed in Section 5.3.1 as well as the types of CV deaths, the types of non-fatal MIs, types of fatal and non-fatal strokes, stent thrombosis and all not assessable cases will be presented. The category of other cardiovascular causes will be presented with subcategories of "other assessable CV causes" and "presumed CV death".

7.8.1.8 Events qualifying for external adjudication by the Clinical Event Committee (CEC) for pancreatic events (CECP)

Based on the CECP adjudication results, the number of patients for each of the following events will be summarized in frequency tables (overall and by adjudication trigger i.e. lab or AE):

- Acute pancreatitis (with organ failure)
- Acute pancreatitis (without organ failure)
- Chronic pancreatitis (with organ failure)
- Asymptomatic pancreatic hyperenzymemia
- Pancreatic malignancy

The analysis will be performed on TS.

The analysis will be performed using all events from study treatment start until study end and in addition the 'on-treatment + 7 days' approach.

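### Once study drug is stopped, lipase becomes optional at attended visits, yet lab-triggered pancreatic events are tabulated to study end with no report of who was still being tested

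*Protocol*

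**What the plan says.** Protocol 3.1 sets the rule: "Patients who discontinue study drug prematurely should continue study visits until study end. Study assessments may be omitted", "with exception of collection of adverse events, outcome events, concomitant therapy and laboratory testing of creatinine for the calculation of the eGFR". Flow Chart footnote C and sections 3.3.4.1 and 6.2.3 carry the same list. Adverse events, outcome events and concomitant therapy are therefore still collected, and creatinine is the only test on the list. The rule permits omission; it does not require it.

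The tests do not lapse on the day of the stop. Section 3.1 states: "The End of Treatment visit (EOT) activities will be performed when a patient discontinues study medication treatment permanently". For the visit 30 days later, Flow Chart footnote D states: "The follow-up visit may be performed as a phone visit for patients who did not prematurely discontinue study medication", so the telephone option is not open to early stoppers. The Flow Chart marks ECG and safety laboratory at both visits, and Protocol 5.2.3 lists "Clinical chemistry: creatinine and lipase" from Visit 3 through EOT and follow-up.

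For adjudicated pancreatic events, SAP 7.8.1.8 says "The analysis will be performed using all events from study treatment start until study end and in addition" an on-treatment + 7 days version. Results are shown overall and split by whether a laboratory value or an adverse event triggered adjudication. Asymptomatic pancreatic hyperenzymemia is one of the listed categories.

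For the heart, the footnote in Protocol 5.1.1 reads: "Any investigator reported silent MI that is adjudicated and confirmed as being an MI by the CEC will be counted as MI". The primary analysis counts events to study end (Protocol 7.3, SAP 7.4.1), and SAP 6.8.3 makes censoring independent of drug intake.

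**The concern.** An event that only a laboratory value can reveal is counted over a period in which that value need not be measured. Creatinine was kept off drug so that the renal endpoint could follow the ITT principle (rationale in Protocol Section 11, first amendment). The same reasoning applies to lipase if pancreatic events are counted to study end, but lipase was not added to the list.

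Two readings of the pancreatic tables suffer. First, the to-study-end and on-treatment + 7 days versions differ in how often lipase was measured as well as in drug exposure. A lower off-drug rate of lab-triggered events could mean less disease or less testing. Second, if one arm spends more time off drug, that arm loses more detectable events and looks better for a reason unrelated to the pancreas. Pancreatitis is an adverse event of special interest in this trial, so these tables will be read with care.

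Nothing in the readable text offsets this. Missed tests are treated as missing data rather than deviations (SAP 6.2), safety endpoints are not imputed (Protocol 7.4), and no table of lipase or ECG coverage by arm or drug status is planned.

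**Working it through.** **Inputs from the documents.** The off-drug assessment list, the EOT and follow-up schedule, and the counting windows are as set out above. For context, the 611-event target reproduces: 4 × (1.960 + 1.282)² / (ln 1.3)² gives 611, with power 90.0%. This point does not dispute that figure.

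**Inputs that are assumed.** The documents give neither the share of follow-up spent off drug nor the share of primary events that would be silent MI. The ranges used are:
- off-drug share of event time (strictly, the part after the EOT and follow-up visits): 15% to 30% per arm;
- silent-MI share of primary events: 2% to 20%;
- off-drug detection: none, or half the on-drug level for lab-triggered events.

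**Formula.** Let s be the share of events found only by the optional test, f_L and f_P the off-drug shares in the linagliptin and placebo arms, and d the off-drug detection relative to on-drug. With equal true rates,

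apparent ratio = [1 − s·f_L·(1 − d)] / [1 − s·f_P·(1 − d)].

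**Lab-triggered pancreatic events (s = 1).**

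| Off-drug share, linagliptin vs placebo | Ratio, no off-drug detection | Events missed | Ratio, half detection | Events missed |
|---|---|---|---|---|
| 15% vs 15% | 1.000 | 15% | 1.000 | 7.5% |
| 25% vs 25% | 1.000 | 25% | 1.000 | 12.5% |
| 20% vs 25% | 0.80/0.75 = 1.067 | 22.5% | 0.900/0.875 = 1.029 | 11.2% |
| 25% vs 20% | 0.75/0.80 = 0.938 | 22.5% | 0.875/0.900 = 0.972 | 11.2% |
| 20% vs 30% | 0.80/0.70 = 1.143 | 25% | 0.90/0.85 = 1.059 | 12.5% |
| 30% vs 20% | 0.70/0.80 = 0.875 | 25% | 0.85/0.90 = 0.944 | 12.5% |

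Equal off-drug time loses events but leaves the ratio at 1.

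**Silent MI within 3P-MACE (no off-drug detection).**
- s = 5%, 20% vs 25%: (1 − 0.0100)/(1 − 0.0125) = 1.0025, with 1.1% of events missed.
- s = 10%, 20% vs 30%: 0.98/0.97 = 1.010, with 2.5% missed.
- s = 20%, 20% vs 30%: 0.96/0.94 = 1.021, or 0.979 with the arms reversed, with 5% missed. This is the extreme of the assumed range.

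**The case against.** The plan has more protection than the off-drug list alone suggests. Lipase and ECG are scheduled at EOT and 30 days later, so any gap opens only after that. The SAP already gives two windows and separates laboratory from adverse-event triggers, which isolates the affected category. The tables are descriptive; Protocol 7.3.3 plans no formal inference for safety comparisons. The adjudication triggers are set in the CEC charter, which is not available here, and parts of the SAP cannot be read, so further handling cannot be ruled out. Finally, Protocol 3.3.4.1 offers lighter follow-up on purpose to keep off-drug patients in the trial; extra mandatory procedures could push some to telephone contact and lose their creatinine.

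Most of this stands, and it rules out three stronger readings.

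- A reader might infer that the plan treats ascertainment as constant. It does not: the on-treatment + 7 days and by-trigger displays, and the TS+30 sensitivity analyses for the primary and key secondary endpoints (Protocol 7.3.1), say otherwise.
- Because of the instruction "If pancreatitis is suspected, the study treatment should be stopped", a reader might infer that lipase disappears in just the patients with pancreatic disease. The episode that prompts the stop is followed by EOT and follow-up visits with lipase. It is also reportable as an adverse event of special interest and can enter adjudication by that route. Only later, laboratory-only findings are exposed.
- A reader might want the scheduled ECG made mandatory off drug. That is a genuine retention trade-off, and the gain for the primary endpoint is too small to settle it.

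What remains is that neither display shows how much lipase testing lies behind the off-drug counts. SAP 6.8.3 censors endpoints based only on laboratory data at the last sample of the parameter, but that rule serves time-to-event analyses and does not reach the frequency tables in 7.8.1.8.

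**Conclusion.** The point holds for lab-triggered pancreatic events, as an inexpensive improvement rather than a flaw in the confirmatory analysis. Detection can fall once lipase becomes optional, and the two planned windows cannot be compared cleanly without knowing who was tested. The apparent ratio between arms is about 1.07 or 0.94 at assumed off-drug shares of 20% vs 25%, and 1.14 or 0.875 at 20% vs 30%, both with no off-drug detection. It is closer to 1 if optional testing continues in part, and exactly 1 if off-drug time and testing are the same in both arms. No passage shows that off-drug time will differ.

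A reader might go further and conclude that silent MI puts the primary result at risk. The documents do not support that. The shift is at most about 2% on the hazard ratio at the extreme of the assumed inputs, against a margin of 1.3, and about 0.25% in the milder case shown above. Nor can missed silent MIs be subtracted from 611: the trial runs until 611 patients have confirmed events (Protocol 3.1 and 7.1), so missed events would delay that count, not shrink it.

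**What to change.** **Protocol.** In Flow Chart footnote C and sections 3.1, 3.3.4.1 and 6.2.3, add lipase to the assessments that may not be omitted when a patient who has stopped study drug attends a visit. It can be run on the blood already drawn for creatinine, so there is no extra needle and no extra visit.

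**SAP 7.8.1.8.** Beside both existing windows, show lab-triggered events together with lipase coverage by arm and drug status: the number of patients with lipase measured and the patient-time covered by it, with the rule for covered time stated. Report ECG coverage by arm and drug status in the same way, so that the silent-MI contribution can be judged without changing the ECG schedule.

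**Cost.** A small added laboratory cost and one more table. The protocol change cannot reach patients followed only by telephone; the coverage table will at least show how many there are. If visits have already ended, the SAP part still works, because it uses only data already collected.

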### **3.1.1 Administrative structure of the trial**

The study is sponsored by Boehringer Ingelheim (BI).

Co-ordinating Investigators who will (co) chair the Steering Committee (SC) will be nominated.

Documents on principal investigators and other important participants at each site, especially their curricula vitae, will be filed in the Clinical Trial Master File (CTMF).

CRO's will be assigned for central laboratory, interactive response technology (IRT), ECG analyses and conduct of the trial.

The following committees will participate in the conduct of the trial, their specific functions are summarised below:

#### Steering Committee

A SC will have a scientific and clinical advisory function in the study. The SC is comprised of university- and sponsor-based scientists with clinical and methodological expertise. Details on the composition of the committee, its procedures and interactions are provided in a separate SC Charter.

